## SUMMARY OF CHANGES

#	Section	Page(s)	Change	Justification
1.	1.2.1	16	Corrected sentence	Previously incomplete
2.	4.5	24	Screening period changed from 10 days to 28 days	Clarified to reflect schedule of events
3.	5.3.1	28	Clarified required duration of contraception after treatment	Inconsistency between exclusion criteria and description in 5.3.1
4.	6.2.2	32	Removed LDH and magnesium from biochemistry panels	These are not part of normal lab panels and are not routinely collected
5.	6.8	34	Updated schedule of events per standard of care	Labs and time points were not represented accurately
6.	Title Page	1	Updated list of investigators and statistician	Include only investigators who are participating in the study and have received training/delegation from PI

[figure not shown]
## SYNOPSIS

Study Title	A pilot study to assess feasibility of stereotactic body radiation therapy for hepatocellular carcinoma patients awaiting liver transplantation
Protocol #	18810
Study Center	OHSU, single-site
Clinical Phase	Pilot
Investigational Component(s)	Radiation Therapy
Interventional Study Type	Single-arm
Précis	
Liver transplantation (LTx) is the best treatment for patients with hepatocellular carcinoma (HCC) and Child-Pugh (CP) B or C cirrhosis, as both conditions can be very effectively treated at once. As liver transplantation wait-lists can be many months, liver directed therapies (LDTs) are essential as oncologic temporizing measures to bridge patients to transplantation. However, due to the fear of further hepatic decompensation, many patients with advanced cirrhosis are excluded from receiving LDTs. This study hypothesizes that liver stereotactic body radiation therapy (SBRT) can be of safe and practical use in this fragile patient population and may result in the reduction of transplantation drop-out rates. The overall goal of this pilot proposal is to evaluate the feasibility of bridge-to-transplantation liver SBRT in hepatocellular carcinoma patients with Child-Pugh B8 or higher cirrhosis.

Primary Objectives	Assess the use of SBRT in HCC patients with advanced liver cirrhosis as a feasible approach to providing localized disease control that adequately suffices liver transplant eligibility criteria.
Secondary Objectives	Assess preliminary efficacy and toxicity in HCC patients with advanced cirrhosis following liver SBRT
Exploratory Objectives	
Assess quality of life (QoL) in HCC patients with advanced cirrhosis following liver SBRT
 
Examine SBRT-related histopathologic changes in explanted livers of patients with advanced cirrhosis.

Primary Endpoints	
 
1. Proportion of participants that are transplant eligible 1 year following SBRT
 

Secondary Endpoints	
 
1. Incidence of progressive disease within or at the planned tumor volume (PTV) margin (i.e. local control)
 
2. Incidence of progressive disease within any section of the liver, including the PTV (e.g. intrahepatic disease free survival)
 
3. Incidence of progressive disease outside of the liver (e.g. extrahepatic disease free survival)
 
4. Overall Survival
 
5. Proportion of participants that proceed to transplantation
 
6. Incidence of non-classical radiation-induced liver disease (RILD), defined as grade 4 aspartate aminotransferase or alanine aminotransferase elevation, or an increase in CP score of <math>\geq 2</math> within 1 week to 3 months after completing SBRT.
 

	7. Incidence of liver toxicity per CTCAE v5.0 within 1 week to 3 months after completing SBRT.
Exploratory Endpoints	
 
1. QoL scores for EORTC QLQ-C30 questionnaire
 
2. QoL scores for Functional Assessment of Cancer Therapy-Hepatobiliary (FACT-Hep) questionnaire
 
3. At time of transplantation, histopathologic changes in irradiated tumor sites relative to uninvolved liver tissue will be assessed
 

Number of Participants	15
Duration of Therapy	SBRT will be administered as 5 fractions every other day (~10 day)
Duration of Follow Up	Time of progression, or transplantation, or 2-years after last SBRT dose, whichever occurs first
Key Inclusion Criteria	
 
1. Participants aged <math>\geq 18</math> years
 
2. Patient diagnosed with HCC and recommended for LTX
 
3. Meets clinical criteria for eligibility for SBRT to the target lesion
 
4. Childs-Pugh Class B8 or higher
 
5. Eastern Clinical Oncology Group performance status <math>\leq 2</math>
 
6. Safe radiation treatment planning parameters that adhere to all organs at risk constraints per section 5.1 of the protocol. If normal organs at risk constraints (including at least 700cc of uninvolved liver) are unable to be met at the lowest dose modification (30 Gy in 5 fractions), the patient is deemed ineligible for SBRT and deemed a screen failure.
 

Key Exclusion Criteria	
 
1. Prior radiotherapy to the upper abdomen or radioembolization of the liver
 
2. Prior SBRT to the target lesion, RFA, or LTX
 
3. Active GI bleed within 2 weeks of study enrollment
 
4. Contraindication to receiving SBRT
 
5. Contraindication to both contrast enhanced MRI and contrast enhanced CT (i.e. unable to undergo follow-up imaging or SBRT treatment planning)
 
6. Women who are pregnant
 

Investigational Product	SBRT
Statistical Considerations	This is a pilot study with no formal hypothesis test but to assess a preliminary estimate of feasibility. A sample size of 15 patients will ensure that at least one SBRT ineligible participant is encountered (at a 95% confidence interval).

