##### 3.2.2 SECONDARY ENDPOINTS

Endpoint	Start	End
1. Localized control rate: Incidence of progressive disease within or at the planned tumor volume (PTV) margin		Time of progression, transplantation, death or 2-years after last SBRT dose, whichever occurs first.
2. Incidence of intrahepatic progressive disease		
3. Incidence of extrahepatic progressive disease		
4. Proportion of participants that proceed to transplantation	First dose of SBRT	
5. Overall Survival		Time of death or 2-years after last SBRT dose
6. Incidence of non-classic RILD, defined as grade 4 aspartate aminotransferase or alanine aminotransferase elevation, or an increase in CP score of $\geq 2$ within 1 week to 3 months after completing SBRT (Appendix A)		3 months after last SBRT dose

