## 4.6 PARTICIPANT WITHDRAWAL OR DISCONTINUATION

Participants are free to withdraw consent and discontinue participation in the study at any time and without prejudice to further treatment. If a participant no longer wants to receive investigational product, but is willing to come for follow-up appointments, the participant's request should be honored, if possible. The following are examples demonstrating why a participant's treatment might be discontinued.

- Toxicity precludes further study treatment.
- There is a need for any treatment not allowed by the protocol.
- The participant fails to meet the criteria for study treatment.
- Pregnancy or intent to become pregnant.
- Disease recurrence or progression.
- Investigator's discretion.

No further participant contact should be made if the participant withdraws consent for participation in the study. Information about the reason(s) for discontinuation and collection of any new or ongoing adverse events (AEs) should be collected at the time the participant withdraws consent.

For all other reasons for discontinuation from the study treatment phase, the participant should return to the clinic for the end of treatment (EOT) visit according to Section 6.8.

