##### 6.1.6.1 Radiation-induced liver toxicity

Radiation-induced liver disease (RILD) is defined as either classical or non-classical RILD. Classical RILD (typically occurring in patients without background liver dysfunction or cirrhosis) is characterized as the presence of nonmalignant ascites and anicteric elevation of alkaline phosphatase level twice the upper level of normal or baseline value occurring between 2 weeks and 3 months after the completion of irradiation. Non-classical RILD (typically occurring in patients with baseline liver dysfunction or cirrhosis), occurs is defined as grade 4 AST and/or ALT elevations, or an increase in CP score of  $\geq 2$  within 1 week to 3 months after completing SBRT.

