### 9.1 ANALYSIS POPULATIONS

Safety analysis set: All participants will be evaluable for toxicity from the time of their first fraction of SBRT.

Efficacy analysis set: The analysis population to assess transplantation eligibility (i.e., Milan criteria) and efficacy endpoints (e.g., localized control rate, intrahepatic progression, extrahepatic progression and overall survival), will include only participants who have received at least 85% of the prescribed SBRT dose (i.e., 85% Level 0 = 34 Gy; 85% Level -1 = 30 Gy; 85% Level -2 = 25.5 Gy).

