#### 9.2.3 ANALYSIS OF THE SECONDARY ENDPOINTS

Using the efficacy analysis set, the estimate of local control rate, intrahepatic progression free survival, and overall survival, will be plotted using Kaplan-Meier curve and reported with median survival and 95% CI if available. Using the same efficacy analysis set, the proportion of participants that proceed to transplantation, will be measured and reported with 95% CI.

Non-classic RILD, liver toxicity defined as a  $\geq 2$  increase in CP score (**Appendix A**), and liver toxicity per CTCAE v5.0, will be estimated along with an exact CI using the safety analysis set.

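### The CTCAE liver-toxicity endpoint borrows the RILD window, which omits on-treatment and first-week events and leaves early stoppers without a window, in conflict with Sections 9.1 and 6.3

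*Combined protocol and SAP*

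**What the plan says.** Two hepatic safety endpoints in the synopsis share one counting window. Endpoint 6 is non-classical RILD. Endpoint 7 is "Incidence of liver toxicity per CTCAE v5.0 within 1 week to 3 months after completing SBRT". Section 6.1.6.1 gives the same window, "within 1 week to 3 months after completing SBRT", as part of the cited definition of non-classical RILD.

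Other sections do not fit that window:

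- Section 9.1 defines the safety set: "All participants will be evaluable for toxicity from the time of their first fraction of SBRT".
- Section 6.3 removes from analysis only toxicity that arises before treatment begins.
- Section 9.2.3 covers non-classical RILD, a Child-Pugh rise of 2 or more, and CTCAE liver toxicity. These "will be estimated along with an exact CI using the safety analysis set". It states no window for any of the three.
- The table in Section 3.2.2 shows a start of "First dose of SBRT", apparently a merged cell covering all rows, and ends RILD at "3 months after last SBRT dose". Endpoint 7 is absent from this table, so its window is stated only in the synopsis.

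Stopping SBRT early is foreseen. Section 4.6 lists "Toxicity precludes further study treatment" among the reasons, and Section 5.2 removes participants after a long interruption.

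**The concern.** A window that opens one week after SBRT is completed makes sense for a named syndrome with a known latency. No section explains why it should also govern liver toxicity of every kind. Under the literal text, a hepatic event confined to the treatment period or the following week falls outside endpoint 7. A participant who never completes SBRT has no date from which to start the window.

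Section 1.3 gives fear of further decompensation as the reason many of these patients are denied liver-directed therapy, and says the pilot is meant to shape a larger multi-institutional trial. Treatment-limiting hepatic events are therefore among the most informative this study can observe. As the text stands, one analyst could apply the synopsis window and another could follow Section 9.1 from the first fraction. Both could defend the choice, and the two rates could differ.

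**Working it through.** **The plan's own figure.** The only computed design figure is N = 15 in Section 9.3.1. With an ineligibility probability of 0.20 and 95% confidence, ln(0.05)/ln(0.80) = 13.43, which rounds up to 14. At n = 15 the chance of at least one ineligible participant is 1 − 0.80^15 = 0.965. The stated 15 is adequate. It has no bearing on the toxicity endpoints, for which the plan gives no precision figure.

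**Length of the omitted period.** Count from day 1 (first fraction) to the day before the 1-week mark. Take 3 months as 91 days.

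| Last fraction | Source | Days omitted | Day 1 to 3 months after last fraction | Share |
|---|---|---|---|---|
| Day 9 | Section 6.8 | 9 + 6 = 15 | 9 + 91 = 100 | 15% |
| Day 10 | Monday/Wednesday/Friday spacing | 10 + 6 = 16 | 10 + 91 = 101 | 16% |
| Day 14 | Assumed upper end of the two weeks in Section 5.2 | 14 + 6 = 20 | 14 + 91 = 105 | 19% |

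**Effect per participant.** One participant is 1/15 = 6.7 percentage points. The number affected is unknown, so the table shows a range. It assumes 3 events counted under the synopsis window and 0, 1 or 2 further participants with an event only outside it. Intervals are Clopper-Pearson.

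| Outside the window (assumed) | Rate with those events counted | Exact 95% CI |
|---|---|---|
| 0 | 3/15 = 20.0% | 4.3 to 48.1 |
| 1 | 4/15 = 26.7% | 7.8 to 55.1 |
| 2 | 5/15 = 33.3% | 11.8 to 61.6 |

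For scale, the 20 to 30% RILD rate in Section 8.4.1 implies 15 × 0.20 = 3 to 15 × 0.30 = 4.5 events. One uncounted case is then a sizeable fraction of the total, although every interval is wide.

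**What a wider window could capture.** Sections 6.1.6 and 8.5 record adverse events from consent to 3 months after SBRT, so the early period is covered for reported events. Section 6.8 schedules hematology, biochemistry and coagulation at screening and then at follow-up. The first follow-up is at 6 weeks (weeks 2 to 10 with the ±4-week allowance). The next is at about 6 + 13 = 19 weeks (weeks 15 to 23). Only one scheduled laboratory assessment falls within 3 months of SBRT, and none falls in the omitted period.

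**The case against.** The strongest reply is that the sections conflict, and that nothing in them amounts to a rule discarding early events. Section 9.2.3 imposes neither a 1-week start nor a completion condition. Section 3.2.2 already ends RILD relative to the last dose, so early stoppers can be given a window. This stands. A reader might infer that hepatic toxicity during treatment, or in participants who stop for it, can never count and is scored as a non-event. No section says so.

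Other parts of the reply also stand:

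- An early event that persists into the window would still count, for example a Child-Pugh rise still present at 6 weeks. Only participants whose sole event lies outside the window are lost.
- For RILD the 1-week bound is part of a cited definition. In that sentence it may attach only to the Child-Pugh rise and not to the transaminase criterion. Endpoint 7 has no such ambiguity.
- A reader might stretch the gap to nine weeks (4 × 14 + 7 = 63 days) from the interruption limit in Section 5.2. Section 6.4 and the Section 6.8 footnote limit visit delays to 7 days. Those passages need reconciling, and nine weeks is not a fair description of the plan.
- Bias is not certain to be downward in every case. If Section 9.4 were used to drop an early stopper without an event, 3/15 = 20.0% would become 3/14 = 21.4%. Section 5.2 also replaces some removed participants, so the safety set could exceed 15.
- Early events still reach safety oversight through adverse event recording, the 30-day evaluation in Section 6.6, the pause rule in Section 8.7 and monitoring committee review.

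None of this removes the conflict for endpoint 7. Its only stated window does not match the safety set in which it is to be analysed.

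**Conclusion.** The point holds as a conflict between stated rules. The synopsis window for endpoint 7 leaves out roughly the first 15 to 20 days of an on-schedule course and gives early stoppers no time zero, while Sections 9.1 and 6.3 bring in all toxicity from the first fraction. Applied literally in the safety set, it can understate the liver-toxicity rate by 6.7 points for each participant whose only hepatic event falls outside it. This assumes 15 participants in the safety set, with affected participants kept in the denominator. The documents give no basis for how many there will be, so no total bias can be stated. These are descriptive secondary endpoints without a hypothesis test. The case for settling the rule before analysis is that hepatic safety is a central question for this population and the correction is cheap.

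**What to change.** 1. Count CTCAE liver toxicity (endpoint 7) from the first fraction to 3 months after the last fraction received. State this in the synopsis and Section 9.2.3, and add endpoint 7 to the Section 3.2.2 table.
2. Keep the 1-week to 3-month window for non-classical RILD, but replace the completion anchor with the last SBRT fraction received in the synopsis, Section 3.2.2 and Section 6.1.6.1. This agrees with the end already given for RILD in Section 3.2.2 and gives early stoppers a window.
3. State in Section 9.2.3 that the separate Child-Pugh-increase analysis uses the same RILD window, and list hepatic events before the 1-week mark on a separate line of the table.

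The cost is wording only, with no change to sample size or data collection. There are two downsides. The reported liver-toxicity rate may be higher. The change also recovers only recorded adverse events and unscheduled laboratory results, because no blood tests are scheduled between screening and the 6-week visit. That is why the Child-Pugh analysis stays on the RILD window.

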## 4.7 OFF-STUDY CRITERIA

Criteria that can take a participant off-study include:

- Participant requests to be withdrawn from study without further follow-up,
- Completed study follow-up period,
- Progression of disease,
- Death,
- Screen failure,
- Investigator's discretion

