#### **6.5 FOLLOW-UP**

Participants will be followed and disease assessments will take place 6 weeks following completion of SBRT, then every 3 months up until enrollment on hospice or death, or 2 years from time of last SBRT dose, whichever occurs first. Follow-up visits will be consistent with standard of care, and assessments are listed in Section 6.8. Any participants removed from protocol therapy for unacceptable AE(s) will be followed until resolution or stabilization of the AE.

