## 6.8 SCHEDULE OF EVENTS

Visit Days	Screening	Treatment					Follow-Up B (±4 weeks)	
	Days -28 to -1	Days † (+7 days)						
		1	3	5	7	9*		
SBRT A		X	X	X	X	X		
Informed consent	X							
Inclusion/exclusion criteria	X							
Medical history	X						X B	
Prior/concomitant medications	X						X B	
Physical Examination C	X						X B	
Radiographic Imaging	X	X D	X D	X D	X D	X D	X E	
Hematology F	X						X B	
Biochemistry G	X						X B	
Coagulation	X						X	
Pregnancy test	X							
Fiducial placement (if needed)	X							
AE assessment	X	X					X	
EORTC QLQ-30	X						X B	
FACT-Hep	X						X B	

† Starting on day 1, SBRT dose fractions are given every other day (i.e., Monday-Friday), but not administered on Saturdays, Sundays, or holidays. Dosing interruptions because of weekends and holidays will be recorded in CRF.

\*Day 9 study assessments of radiographic imaging and AE collection will serve as Early Termination and/or End of Treatment Visit.

A Scheduled SBRT visits may be delayed by no more than 7 days between each visit, or may occur earlier than scheduled by no more than 3 days.

B Follow-up assessment to occur 6 weeks following completion of SBRT then every 3 months up to 2 years post SBRT therapy

C All physical exams will include assessing weight, vital signs, and ECOG performance status. Height will be measured at screening visit only.

DCone-beam CT will be obtained prior to each SBRT fraction.

E Participants will undergo surveillance imaging (e.g., CT scan) 6 weeks following completion of SBRT and then every 3 months for the first 2 years.

F Hemoglobin, platelets and white cell count with differential white count

G Biochemistry to include renal (creatinine, urea, sodium, potassium) and liver function (AST, ALT, bilirubin)

HAEs and laboratory safety measurements will be graded per NCI CTCAE version 5.0 as well as definition of radiation-induced liver disease (Child-Pugh elevation of 2 or more). All AEs, whether gradable by CTCAE or not, will also be evaluated for seriousness. Record all AEs and SAEs occurring from the time of consent signing to 3 months following the completion of SBRT.

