### **9.4 HANDLING OF MISSING DATA**

Every attempt will be made to obtain data at the defined time points as described in the primary and secondary endpoints. For time points that have no data, we will evaluate whether or not the other time points can be used to fulfill the primary and secondary data. If the data are not sufficient to analyze specific endpoints, the participant's data may be excluded entirely or partially, depending on the specific endpoints in question and in consultation with the biostatistician. No missing data will be imputed. Whenever possible, all available data will be included in the analysis. A sample size for each analysis will be clearly stated along with the reason for exclusion, if any participant is excluded from the analysis due to missing data.

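### Four passages end follow-up at different points, so deaths could go uncollected if a shorter rule is applied; separately, the progression endpoints have no stated handling of transplantation and death

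*Combined protocol and SAP*

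**What the plan says.** **End of follow-up**

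- Synopsis, Duration of Follow Up: "Time of progression, or transplantation, or 2-years after last SBRT dose, whichever occurs first".
- Section 4.7: "Criteria that can take a participant off-study include", followed by a list that contains "Progression of disease". The wording is permissive, and transplantation is not on the list.
- Section 6.5: visits at 6 weeks, "then every 3 months up until enrollment on hospice or death, or 2 years from time of last SBRT dose, whichever occurs first".
- Section 6.8, note B: "Follow-up assessment to occur 6 weeks following completion of SBRT then every 3 months up to 2 years post SBRT therapy", with no stop at progression, transplantation or hospice.
- Section 3.2.3: quality of life is collected until death or 2 years, again with no stop at those events.

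**Overall survival.** Section 3.2.2 ends it at "Time of death or 2-years after last SBRT dose", and section 7.3.5 agrees on the end. Section 9.4 adds a general commitment: "Every attempt will be made to obtain data at the defined time points as described in the primary and secondary endpoints". It also rules out imputation.

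**Progression endpoints.** Section 3.2.2 words them as incidence, in a window that closes at "Time of progression, transplantation, death or 2-years after last SBRT dose, whichever occurs first". The synopsis uses incidence, local control and disease-free survival for the same items. Sections 7.3.3 and 7.3.4 end their windows at progression, transplantation or 2 years and do not mention death. Section 7.3.4 labels its endpoint progression-free survival although only disease progression is an event. Section 9.2.3 gives Kaplan-Meier for local control, intrahepatic progression-free survival and overall survival. It states no censoring rule and no method for extrahepatic progression.

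**The concern.** Overall survival needs vital status after progression and after transplantation. Staff who apply the synopsis line or section 4.7 would stop collecting it and still be within the protocol, because nothing ranks the endpoint definitions above those passages. Section 6.5 raises the same question at hospice enrolment, shortly before many deaths would be expected. Deaths that are not collected as they occur may be hard to recover later.

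The progression endpoints have a different gap. Transplantation and death prevent later progression from being seen, and both are likely to be common in this population. A Kaplan-Meier curve that censors them answers a different question from how often progression occurs. Section 1.3 wants estimates of bridging efficacy relative to historical controls, and any such comparison needs one stated definition per endpoint.

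**Working it through.** **The plan's own figure.** The plan gives no number on this point. Its only design calculation, 15 patients to see at least one SBRT-ineligible case at 20% probability, reproduces (1 - 0.8^15 = 0.965) and is not affected.

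**Overall survival: model.** Constant yearly hazards: death before progression or transplantation d, progression p, transplantation t, death after progression m, death after transplantation u, with L = d + p + t. With no transplantation after progression, true 2-year survival is

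exp(-2L) + p[exp(-2m) - exp(-2L)]/(L - m) + t[exp(-2u) - exp(-2L)]/(L - u).

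The Kaplan-Meier limit under the synopsis rule is exp(-2d). For a stop at progression only, it is the exponential of minus the integrated death hazard among people alive and unprogressed or transplanted.

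**Inputs.** One value has a document source: d = 12 ln2/17 = 0.489, from the 17.0-month median for Child-Pugh B in section 1.2.1, which is not a transplant-listed B8-or-higher cohort. All other hazards are assumptions. The grid has 64 combinations: d 0.30 or 0.489; p 0.15 or 0.30; t 0.20 or 0.60; m 1.5 or 3 times d; u 0.05 or 0.15; transplantation after progression at zero or half rate.

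**One case in full.** d = 0.30, p = 0.30, t = 0.20, m = 0.90, u = 0.15, none transplanted after progression, so L = 0.80. True survival = 0.202 + 0.30(0.165 - 0.202)/(-0.10) + 0.20(0.741 - 0.202)/0.65 = 0.202 + 0.110 + 0.166 = 0.478. Synopsis rule: exp(-0.60) = 0.549, or +7.1 points. This is the grid's upper extreme for that rule. The lower extreme (d 0.489, p 0.15, t 0.60, m 1.5 times d, u 0.05, half rate) has true 0.551 against 0.376, or -17.5 points.

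| Rule applied to data collection | Shift in 2-year survival over the grid |
|---|---|
| OS definition followed | 0 |
| Synopsis (progression or transplantation) | -17.5 to +7.1 points |
| Progression only | +1.8 to +11.8 points |

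The synopsis result depends heavily on the transplant rate: the median shift is -1.0 at t = 0.20 and -9.5 at t = 0.60. For context, section 1.2.1 reports 13 of 51 patients (25%) with B8 or higher eventually transplanted, in a cohort not described as transplant-listed.

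A second set of assumptions (base case p 0.30, t 0.40, d 0.30, m 1.0, u 0.05) has true 54.1%, synopsis 54.9% and progression-only 66.5%. Its unequal-hazard cases range from -10.3 to +14.0 and from +1.4 to +21.6 points. With equal death hazards in all states, both shifts are 0. Simulating 15 people in that base case, the standard deviation of the 2-year estimate rises from 12.8 points with full follow-up to 21.0 under the synopsis rule, although the biases nearly cancel.

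For scale, the exact 95% interval for 8 of 15 is 27% to 79%.

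**Progression.** Section 1.2.1 gives 82% local control at 2 years for Child-Pugh B, so the hazard is h = -ln(0.82)/2 = 0.0992 and 1 - KM = 18%. With a competing hazard c for transplantation plus death (assumed), cumulative incidence = h/(h + c) x [1 - exp(-2(h + c))]:

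- c = 0.30: 13.7%
- c = 0.60: 10.7%
- c = 1.0: 8.0%

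**The progression-free survival label.** With assumed intrahepatic progression at 0.10 and death at 0.30 per year, the 2-year value is exp(-0.20) = 82% if death is censored and exp(-0.80) = 45% if it is counted. No passage says which applies.

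**The case against.** The best defence is that overall survival is already properly defined. Sections 3.2.2 and 7.3.5 end it at death or 2 years, sections 6.5 and 6.8 continue visits past progression and transplantation, section 4.7 only permits an exit, and section 9.4 commits to obtaining endpoint data. That stands: the plan as a whole does not make overall survival wrong. A reader might infer that it does, but the error arises only if a shorter passage is applied to data collection.

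The sizes are also open to challenge. They come from chosen hazards, and a median or count over such a grid is not a probability. The plan names a Kaplan-Meier curve and median survival, not a 2-year rate; 2 years is used here only as a scale. No size is given for the hospice stop, because the documents offer no figure for the share of deaths that would be lost.

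A reader might also infer that Kaplan-Meier local control is invalid. It is not: it is a sound net estimate under independent censoring, and section 7.3.3 defines local control as absence of progression. Nowhere does the plan say it will report 1 - KM as incidence. What remains is that two passages name incidence and no analysis delivers it.

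Two further readings carry little weight. The 3.2.2 table appears to close the transplant-proportion window at progression, which would exclude later transplants, but that may be an artefact of the extracted layout and is worth at most 0.8 of 15 people in the grid. The start of overall survival differs (first dose in 3.2.2, after 85% of the dose in 7.3.5). Since 4 of 5 fractions is 80%, the gap is about 8 to 14 days.

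**Conclusion.** The conflict over the end of follow-up is real and lies in current text. Its effect on overall survival is conditional: none if vital status is collected to 2 years; upward bias if collection stops at progression or hospice and death is more frequent afterwards; bias of unpredictable sign, with lost precision, under the synopsis rule. The illustrative sizes, about -18 to +7 points (synopsis) and +2 to +12 (progression only), rest on assumed hazards. Other reasonable choices move them, and they are generally smaller than sampling error at 15 people.

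The progression endpoints need a stated target and a stated handling of transplantation and death. If 1 - KM were read as incidence it would overstate local progression, illustratively 18% against 8% to 14%.

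Severity is minor to moderate. The endpoints are secondary and descriptive, there is no hypothesis test, and nothing here bears on the primary endpoint or the sample size. Confidence is high in the textual conflict and low in any particular size.

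**What to change.** 1. Reconcile the synopsis and sections 4.7, 6.5 and 6.8 on when follow-up ends.
2. Whichever end is chosen for visits, state that vital status and transplant status are collected by chart or telephone to 2 years after the last SBRT dose, regardless of progression, transplantation or hospice enrolment, unless consent is withdrawn. State that overall survival is not censored at those events.
3. In section 9.2.3, report local, intrahepatic and extrahepatic progression as cumulative incidence with transplantation and death as competing events. The Kaplan-Meier local control curve may stay alongside.
4. Make sections 7.3.3 and 7.3.4 agree with 3.2.2 on death. Either count death as an event in intrahepatic progression-free survival or rename the endpoint.
5. As housekeeping, use one start for overall survival in 3.2.2 and 7.3.5, and state plainly that the transplant-proportion window does not close at progression.

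The cost is wording changes, brief status checks in about 15 people, and a little more analysis with a standard competing-risk routine.
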